Unique Protocol ID: No.2024018

Official Title:

Transcranial electrical stimulation combined with interim testing promotes temporal memory in patients with schizophrenia

Document Title: Study Protocol

Date of the Document: 2024/07/15

Study Protocol

Transcranial electrical stimulation combined with interim testing promotes temporal memory in patients with schizophrenia

1. Introduction

The human brain processes sequential information all the time, whether it is verbal communication, action implementation or situational memory, which essentially involves the representation of temporal information [1]. Temporal memory is an individual's memory of the order in which events occur, and is an important foundation for our correct understanding of the world and for memory and reasoning [2]. Research has shown that people with schizophrenia have impaired temporal memory, as evidenced by the patient's ability to recognize stimuli and their inability to recall information in sequence [3–5], which is consistent with pathological features such as thinking in schizophrenia[6].

Interim testing, a behavioral technique, produces forward testing effects by extracting non-target information, thus promoting the retention of target information (new information) [7,8]. tDCS is a neuromodulation technique involving non-invasive, low-intensity electrical stimulation of the cortical regions, modulating spontaneous neuronal activity in the stimulated area [9]. Previous studies have shown the benefits of using interim testing alone [7,8,10] and tDCS alone [11–13] in promoting memory retention in both healthy and clinical populations. However, there is limited research on the combined effects of these two techniques on spatial memory retention. Previous studies have found that combining cognitive training with anodal tDCS treatment of the L-DLPFC can improve visual-spatial memory and episodic memory retrieval [11,14], confirming the feasibility and efficacy of combining behavioral techniques

with neuromodulation techniques to enhance spatial memory retention. Therefore, the present study investigated the facilitation of temporal learning in patients with schizophrenia by a combined ad hoc test of two stimuli, tDCS and transcranial alternating current stimulation (tACS), respectively.

This study investigated the effects of an interim test combined with online tDCS and tACS on temporal memory in patients with schizophrenia. Using online tDCS to stimulate the left dorsolateral prefrontal lobe, during which patients learned static visual pictures for temporal memory. Compare the effects of intermediate tests on correct temporal memory in patients with schizophrenia during anodal and sham tDCS and tACS stimulation. It was hypothesized that the pre-test was significantly better than repeated learning for correctness, and that anodal stimuli were significantly more correct than tACS for correctness and false stimuli for correctness.

2. Methods

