2.1 Participants

Seventy-five inpatients with schizophrenia were recruited from the Third People's Hospital of Lanzhou City (Lanzhou Mental Health Center-Psychiatric Medical Rehabilitation and Nursing Home) and grouped in parallel into 3 conditions, with the sample size depending on the effect size in the study of forward test effects in schizophrenia (Cohen's $d = 1.24$), and to observe a significant level of forward test effects ($\alpha = 0.05$; power = 0.80) a minimum of 11 individuals per group is required [15].

Diagnosis and assessment of patients with schizophrenia were conducted by two chief psychiatrists. Neuropsychological background tests included the Montreal Cognitive Assessment (MoCA) for general cognitive function and the Positive and Negative Syndrome

Scale (PANSS) for symptom assessment.

Inclusion criteria for patients with schizophrenia were: (1) meeting DSM-5 diagnostic criteria for schizophrenia; (2) age \geq 18 years, any gender, education level of primary school or above; (3) all patients receiving stable antipsychotic medication treatment, in a stable phase of illness, able to understand testing requirements, and cooperate to complete all study tasks; (4) no history of neurological or other severe physical diseases, no mental retardation; (5) no color blindness, color weakness, normal vision or corrected vision.

Exclusion criteria were: (1) clear cognitive impairment caused by somatic or cerebral organic lesions, such as cerebrovascular disease, traumatic brain injury, etc.; (2) substance dependence or abuse, mental disorders caused by the use of psychoactive substances; (3) history of brain injury or other central nervous system-related organic diseases; (4) obvious risk of suicide or harm to others; (5) participation in similar experiments within the past 30 days.

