2.2 Design

A between-groups experimental design with 2 (Learning condition: Interim testing, Relearning) \times 3 (Stimulation type: tDCS stimulation, tACS stimulation, sham stimulation) was used. The dependent variables were the final recall accuracy and proactive interference.

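### The stated hypotheses are, on their plain reading, two main effects, so both can be confirmed without showing that stimulation adds anything to interim testing

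*Protocol*

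**What the plan says.** The title makes a claim about a combination: "Transcranial electrical stimulation combined with interim testing promotes temporal memory in patients with schizophrenia". The last paragraph of the Introduction repeats it as the aim, "This study investigated the effects of an interim test combined with online tDCS and tACS on temporal memory in patients with schizophrenia", and then sets a task that comes close to an interaction question: "Compare the effects of intermediate tests on correct temporal memory in patients with schizophrenia during anodal and sham tDCS and tACS stimulation".

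The hypothesis sentence that follows has two parts. The first is "It was hypothesized that the pre-test was significantly better than repeated learning for correctness". The second is that "anodal stimuli were significantly more correct than tACS for correctness and false stimuli for correctness", where the false stimuli are evidently the sham condition.

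Section 2.2 crosses two learning conditions with three stimulation types ("Stimulation type: tDCS stimulation, tACS stimulation, sham stimulation") and calls the design between-groups. Section 2.1 plans 75 patients in three parallel conditions and bases the sample size on the forward testing effect alone (d = 1.24). Section 2.5 names a mixed-design ANOVA comparing the two learning strategies under two stimulation conditions, tests at 0.05, and Bonferroni-adjusted post-hoc comparisons. It names neither the interaction nor a contrast within the interim-testing patients.

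**The concern.** Neither hypothesis is conditional on the other factor. In a 2 x 3 layout, the first is then the learning effect averaged over stimulation types. The second is a pair of stimulation contrasts averaged over learning conditions. The title's claim needs something else: that stimulation improves memory in patients who receive interim testing.

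An averaged stimulation effect can come entirely from the relearning patients, for instance if interim testing already yields most of the available gain. The trial could then report both hypotheses as confirmed and conclude in favour of the combination, although tDCS gave tested patients nothing. What is at stake is whether the headline conclusion rests on the comparison that supports it.

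**Working it through.** **Inputs**
- Six cells from the 2 x 3 design (section 2.2).
- 75 patients in three conditions (section 2.1), so 25 per stimulation type. *Assumption:* learning condition is also between patients, giving 25/2 = 12.5, i.e. cells of 12 or 13, and error df = 75 - 6 = 69. The protocol states no cell size.
- Testing effect 1.24 SD, alpha 0.05, power 0.80 (section 2.1). Two-sided tests are assumed.
- Bonferroni for post-hoc comparisons (section 2.5): 0.05/3 = 0.0167 for three stimulation pairs.
- *Assumption:* a tDCS gain g of 0.8, 1.2 or 1.6 SD in relearning and zero in interim testing. The protocol gives no effect size for stimulation.

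**Step 1: the plan's own figure.** n per group = 2(1.960 + 0.842)²/1.24² = 15.70/1.5376 = 10.2, rounded up to 11. This matches section 2.1 (the exact t calculation gives 11.26, i.e. 12). The figure is sound, but it sizes only the testing effect.

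**Step 2: can both hypotheses be true with no stimulation effect in tested patients?** Cell means in SD units:

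| | tDCS | tACS | sham |
|---|---|---|---|
| Interim testing | 1.24 | 1.24 | 1.24 |
| Relearning | 1.24 | 0 | 0 |

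- Learning main effect: (0 + 1.24 + 1.24)/3 = 0.83.
- tDCS minus sham, averaged: (0 + 1.24)/2 = 0.62. tDCS minus tACS: the same.
- tDCS minus sham within interim testing: 0.

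Both hypotheses hold, and the stimulation effect in tested patients is exactly zero. This step uses no sample size.

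**Step 3: how likely is it?**
- Averaged tDCS-sham contrast: g/2, standard error √(2/25) = 0.283.
- Interaction contrast (difference of differences): size g, standard error √(1/12 + 1/13 + 1/12 + 1/13) = 0.566.
- Both ratios equal g/0.566, i.e. 1.41, 2.12 and 2.83. Unadjusted, the two contrasts therefore have the same power.

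The single-contrast powers use the noncentral t on 69 df. The last two rows come from simulating the six cell means with a pooled error variance.

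| Gain g in relearning only | 0.8 | 1.2 | 1.6 |
|---|---|---|---|
| Learning effect, 1.24 - g/3 | 0.97 | 0.84 | 0.71 |
| Averaged tDCS-sham, g/2 | 0.4 | 0.6 | 0.8 |
| Its power at 0.05 | 0.29 | 0.55 | 0.80 |
| Its power at 0.0167 | 0.16 | 0.38 | 0.65 |
| Interaction contrast significant at 0.05 | 0.29 | 0.55 | 0.80 |
| Learning effect, and tDCS above sham and above tACS with Bonferroni | 0.06 | 0.21 | 0.42 |
| The same, with interaction contrast not significant | 0.04 | 0.09 | 0.08 |

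**Step 4: do the hypotheses separate the two situations?** For the means in step 2, full confirmation (here also requiring a significant stimulation F test) has probability 0.229. If tDCS instead adds 0.62 SD in both learning conditions, it is 0.245. The two hypotheses cannot tell these cases apart.

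**Step 5: detectable effects at 80% power** (two-sided 0.05, 69 df; required noncentrality about 2.84):
- Averaged tDCS-sham: 2.84 x 0.283 = 0.80 SD.
- tDCS-sham within interim testing: 2.84 x √(1/12 + 1/13) = 2.84 x 0.400 = 1.14 SD.
- Interaction contrast: 2.84 x 0.566 = 1.61 SD.
- Within interim testing, Bonferroni over two contrasts (0.025 each, noncentrality about 3.14): 3.14 x 0.400 = 1.26 SD.

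**The case against.** The strongest reply is that the right comparison is already within reach. The aim sentence just before the hypotheses asks for the effect of testing under each stimulation type, the design is crossed, section 2.5 speaks of learning strategies under stimulation conditions, and post-hoc comparisons are planned. This stands: a reader should not infer that the protocol ignores the combination. But the aim is not carried into the hypotheses, and a post-hoc contrast need not be the one that decides the claim. Section 2.5 also refers to two stimulation conditions where section 2.2 has three, so the intended comparison cannot be read off.

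It can also be said that the hypothesis sentence never uses the words pooled or main effect and is loosely worded. That is fair, so main effects are described here as the plain reading, not as the protocol's own term. Contrasts and intervals may properly be left to a statistical analysis plan. The mismatch between hypotheses and aim would remain.

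Two stronger inferences are tempting and do not hold. One is that a misleading confirmation is likely, at 0.29 to 0.80. Those are the powers of a single unadjusted contrast; the stated hypotheses also require superiority to tACS and a learning effect. The other is that the interaction would usually miss the problem. Under the same scenario it has the power of the unadjusted averaged effect, and more than that effect after Bonferroni. The scenario is also severe at its upper end: a 1.6 SD gain confined to relearning exceeds the 1.24 SD testing effect, and nothing in the protocol suggests it.

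**Conclusion.** The point holds as a mismatch between the question and the stated hypotheses. Both hypotheses can be true while stimulation adds nothing to interim testing, and no stated rule makes the interaction or a within-testing contrast count towards the combination claim. The algebra needs no assumption about cell sizes.

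The probabilities do need one. Sections 2.1 (three conditions), 2.2 (between-groups) and 2.5 (mixed-design) do not agree on the layout, so the figures rest on six independent cells of 12-13, and on assumed gains confined to relearning. On that basis full confirmation has probability about 0.06, 0.21 or 0.42, and under 0.10 when the interaction contrast must also be non-significant. A significant interaction in the adverse direction would be visible in the output, but it would refute neither hypothesis as worded. A non-significant one, at this cell size, would not show that stimulation helps tested patients.

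The change should be made, since it is cheap and the record shows recruitment as not yet started. The trial can be analysed without it, but its title would not be tied to the contrast that tests it.

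**What to change.** - **Introduction, hypothesis sentence:** add the hypothesis that interim testing with tDCS gives higher accuracy than interim testing with sham, and name interim testing with tACS against interim testing with sham as a second contrast.
- **Section 2.5:** name these two as planned contrasts under the Bonferroni rule already stated, each with a 95% confidence interval. Report the learning-by-stimulation contrast as the test of synergy only.
- **Claim rule:** state that a conclusion about the combination rests on the within-testing contrast, and that the two main effects support only separate claims about testing and about stimulation.

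The cost is a few sentences of text; the contrasts come from the same data and the same ANOVA. The downside is precision: about 1.14 SD is detectable at 80% power before adjustment (about 1.26 SD with Bonferroni over two contrasts), against about 0.80 SD for the averaged effect. The change ties the claim to the right comparison but does not make that comparison well powered for smaller effects.

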2.1 Participants

Seventy-five inpatients with schizophrenia were recruited from the Third People's Hospital of Lanzhou City (Lanzhou Mental Health Center-Psychiatric Medical Rehabilitation and Nursing Home) and grouped in parallel into 3 conditions, with the sample size depending on the effect size in the study of forward test effects in schizophrenia (Cohen's $d = 1.24$), and to observe a significant level of forward test effects ($\alpha = 0.05$; power = 0.80) a minimum of 11 individuals per group is required [15].

Diagnosis and assessment of patients with schizophrenia were conducted by two chief psychiatrists. Neuropsychological background tests included the Montreal Cognitive Assessment (MoCA) for general cognitive function and the Positive and Negative Syndrome

Scale (PANSS) for symptom assessment.

Inclusion criteria for patients with schizophrenia were: (1) meeting DSM-5 diagnostic criteria for schizophrenia; (2) age \geq 18 years, any gender, education level of primary school or above; (3) all patients receiving stable antipsychotic medication treatment, in a stable phase of illness, able to understand testing requirements, and cooperate to complete all study tasks; (4) no history of neurological or other severe physical diseases, no mental retardation; (5) no color blindness, color weakness, normal vision or corrected vision.

Exclusion criteria were: (1) clear cognitive impairment caused by somatic or cerebral organic lesions, such as cerebrovascular disease, traumatic brain injury, etc.; (2) substance dependence or abuse, mental disorders caused by the use of psychoactive substances; (3) history of brain injury or other central nervous system-related organic diseases; (4) obvious risk of suicide or harm to others; (5) participation in similar experiments within the past 30 days.

2.2 Design

A between-groups experimental design with 2 (Learning condition: Interim testing, Relearning) \times 3 (Stimulation type: tDCS stimulation, tACS stimulation, sham stimulation) was used. The dependent variables were the final recall accuracy and proactive interference.

2.3 Devices and Materials

2.3.1 Devices

We utilized the battery-driven direct current stimulation device from NE, Spain. All groups utilized the same electrode montage, with electrode placement following the 10-20

international electroencephalogram system. For tDCS and tACS intervention, 8cm² circular sponge electrodes were employed. The anode was positioned over F3 (i.e., L-DLPFC), and the cathode over Fp2 (i.e., right supraorbital area).

2.3.2 Materials

A chronological memory paradigm from previous research was used [16]. 128 pictures of common objects were selected from a library of standardized color photographs of objects [17] as temporal-sequence learning and testing materials, and a separate practice sequence was set up for subjects to familiarize themselves with the experimental manipulation. According to [18], the picture size was standardized to 350 × 350 (pixels). The 32 sets of sequence pictures were divided into 4 sequences, each of which was a block.

2.4 Procedure

Before the start of the experiment, the experimenter explained the task and experimental procedure of this experiment, and after the participants understood and agreed to it, they entered the practice phase and started the formal experiment after completion. During this period, participants were informed that after learning each sequence, the computer would randomly decide whether the item order would be tested or not. In fact, whether or not they would be tested was a pseudo-randomized setting, and the test group was tested after learning each sequence. The repeat learning group, on the other hand, was required to learn again. The experimental material was presented on a 14-inch laptop display (resolution 1920 × 1080), with subjects facing the monitor at a distance of about 60 cm, and the screen brightness and contrast were such as to avoid causing discomfort to the subjects.

The classical paradigm incorporating the forward testing effect. Participants first learned the item pictures of the first sequence, displaying the picture items individually in the center of the screen, with each item presented for 2 s. The learning phase required participants to memorize the order of the items that appeared in each sequence, and to press the key to select the order in which the probe items were presented. After the first sequence was learned both groups of subjects solved as many simple math problems as possible within 30s (e.g., $22 + 9 = ?$) . Next, subjects in the temporary test condition were presented with the probe item from Sequence 1, presented for 3 s, followed by the presentation of a combinatorial figure consisting of an array of three objects, and participants were asked to select the object that was presented immediately after it (the target item) from the array of three objects. The setup was the same as in Experiment 1. At the end of the test, learning and testing proceeded with Sequences 2 through 4, with the same process as in Sequence 1.

The learning process of the repeated learning group was the same as that of the temporary test group, with the difference that the repeated learning group did not have test items in Sequences 1-3, and followed the process of the learning phase to learn the pictures of the items in Sequences 1-3 again, i.e., the order in which the items were presented. The difference is that after learning once in sequence 4, it is no longer necessary to repeat the learning, but to enter the testing phase, which is the same as the setup of sequence 4 in the temporary testing group. The experimental flow is shown in Figure1.

[figure not shown]

Figure 1. Experiment procedure.

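### Does the learning-phase key press mean that the relearning control is itself tested on order?

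*Protocol*

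**What the plan says.** Four statements in Protocol section 2.4 (Procedure) bear on the point.

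- Learning phase, with no group singled out: "The learning phase required participants to memorize the order of the items that appeared in each sequence", followed directly by "to press the key to select the order in which the probe items were presented".
- Relearning group, first pass: "The learning process of the repeated learning group was the same as that of the temporary test group".
- Relearning group, second pass: it "followed the process of the learning phase to learn the pictures of the items in Sequences 1-3 again".
- Relearning group, testing: "the repeated learning group did not have test items in Sequences 1-3".

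The probe is described as a stimulus on screen at one point only, after the 30-second arithmetic task: "subjects in the temporary test condition were presented with the probe item from Sequence 1, presented for 3 s". The response is then to pick the next object from three alternatives. Both groups take the Sequence 4 test.

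Section 2.2 makes learning condition (interim testing or relearning) one factor of a 2 × 3 between-groups design. Section 2.1 bases the sample size on the forward testing effect alone: d = 1.24, alpha 0.05, power 0.80, at least 11 per group, 75 patients in total.

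**The concern.** Choosing the order of probe items sounds like retrieval, which is what the interim test is meant to supply and the control is meant to lack. If the key press belongs to the learning phase, and the relearning group goes through that phase twice, its patients would make two order responses per sequence in Sequences 1-3. The testing group would also make two, one in learning and one in the interim test. The groups would then differ in the timing and format of retrieval, and no longer in whether retrieval occurs.

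That would give the control part of the active ingredient. The learning effect would be expected to shrink, and with it any interaction between testing and stimulation. Because the sample size rests only on the testing effect, the planned power would be overstated. The text also contradicts itself on its face: a group cannot both make order selections on probes and have no test items.

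**Working it through.** **Step 1: the plan's own figure.** Inputs from section 2.1: d = 1.24, alpha 0.05 (taken as two-sided, since sidedness is not stated), power 0.80. By the normal approximation, n per group = 2(1.960 + 0.842)² / 1.24² = 15.70 / 1.5376 = 10.2, rounded up to 11. The stated minimum is reproduced. A two-sided t-test needs 11.26, rounded up to 12; power at 11 is 0.79.

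**Step 2: what dilution would cost if it occurred.** Suppose the control receives a share f of the testing effect, so that the remaining effect is 1.24 × (1 − f). Equal allocation is assumed: 75/6 = 12.5 per cell and 75/2 = 37.5 per learning condition. Power is for a two-sided t-test.

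| f (assumed) | d | Power, one stimulation arm (12.5 vs 12.5) | Power, learning main effect (37.5 vs 37.5) |
|---|---|---|---|
| 0 | 1.24 | 0.84 | >0.99 |
| 0.25 | 0.93 | 0.61 | 0.98 |
| 0.50 | 0.62 | 0.32 | 0.76 |
| 0.75 | 0.31 | 0.12 | 0.26 |

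No value of f can be taken from the protocol, so the table shows only how sensitive power is. The comparison within one stimulation arm is the exposed one; the main effect withstands mild dilution.

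**Step 3: does the text establish any dilution?** Set side by side, the statements in section 2.4 favour the other reading.

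- *What the learning phase contains.* Pictures appear one at a time for 2 s each. No probe display, set of response options or response window is described there.
- *Where a probe appears.* It comes after the arithmetic task, for 3 s, and for Sequence 1 only in the interim-test condition. A response to probe items needs a probe, and the learning phase as described has none.
- *What the control repeats.* The second pass is described as learning the pictures and their order again. No response is mentioned.
- *What the control does not do.* The absence of test items in Sequences 1-3 is stated expressly. The start of section 2.4 agrees: one group is tested after each sequence and the other studies again.

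Three statements therefore describe a control that only restudies, and half of one sentence suggests otherwise. That half-sentence makes sense as a statement of what participants must eventually do: memorise the order, then answer by key press when probed.

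**Step 4: the literal reading.** Even then the press would fall in the learning phase of both groups, and the delayed three-object test in Sequences 1-3 would remain unique to the testing group. The text does not say whether the press is made from memory, scored or followed by feedback, so its equivalence to the interim test is not shown.

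**The case for a change.** The strongest case for acting is that the control condition defines the contrast and belongs in the protocol. The sentence names the learning phase and participants in general, and the relearning group is said both to share that phase and to repeat it. Someone following the words alone could not satisfy both statements. If the sentence is misplaced, it still sits in the wrong phase, and correcting it costs one line. The protocol lists the trial as not yet recruiting, so a correction could precede data collection.

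Much of this stands. The wording is inconsistent, and rewording would be cheap. What does not stand is the step from loose wording to a tested control. It needs the half-sentence to outweigh an explicit denial in the same section, and it needs the key press to be retrieval from memory, which is nowhere stated. Nor can the loss of power be sized. The shares f are assumed, and d = 1.24 comes from a cited study whose control condition the protocol does not describe, so any similar response there would already be reflected in that figure. Figure 1, which sets out the flow of the experiment, is not available here and may settle the point.

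**Conclusion.** No change to the design or analysis follows. Section 2.4 contains a clerical slip: a phrase about the test response has been attached to the learning phase. The rest of the section specifies a relearning group that studies again and is first tested at Sequence 4, and anyone building or running the task from the whole section would implement that.

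The size of any harm is unknown and most likely nil. The figures of 0.61 for one stimulation arm and 0.98 for the main effect at f = 0.25 hold only if a quarter of the testing effect leaks to the control, and the protocol offers no support for that. The conclusion assumes that the task as programmed matches the section read as a whole. It would need to be reopened only if relearning patients were in fact asked to give order from memory during Sequences 1-3. Moving the phrase to the description of the test would be a courtesy to the reader and would not alter what the trial does or concludes.
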